6.2.5 Non-Measurable Disease

All other lesions (or sites of disease), including small lesions (longest diameter <10 mm or pathological lymph nodes with ≥ 10 to <15 mm short axis), are considered non-measurable disease. Bone lesions, leptomeningeal disease, ascites, pleural/pericardial effusions, lymphangitis cutis/pulmonitis, inflammatory breast disease, and abdominal masses (not followed by CT or MRI), are considered as non-measurable.

Note: Cystic lesions that meet the criteria for radiographically defined simple cysts should not be considered as malignant lesions (neither measurable nor non-measurable) since they are, by definition, simple cysts.

‘Cystic lesions’ thought to represent cystic metastases can be considered as measurable lesions, if they meet the definition of measurability described above. However, if non-cystic lesions are present in the same patient, these are preferred for selection as target lesions.

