1.2.1 Ewing Sarcoma Family of Tumors (ESFT)

The Ewing Sarcoma Family of Tumors (ESFT) is the second most common malignant bone tumor of childhood (1, 2). In the past 25 years since the advent of 5-drug ESFT therapy, there has been very little improvement in overall patient survival particularly for patients with high risk metastatic or relapsed disease (1). Therefore, there exists a great need for agents that target the genes this tumor depends on for survival.

All ESFT tumors have fusion oncogenic transcription factors generated by chromosomal translocations involving the EWS gene and one of the ETS (E26 transformation-specific) family of transcription factors (3, 4). These transcription factors are highly dysregulated and believed to be critical to the biology of these tumors mediating both malignant transformation and progression (5).

In 85% of cases, the fusion transcription factor is EWS-FLI1 usually generated by the t(11;22)(q24;q12) chromosomal translocation (4). This transcription factor contains the binding domain of FLI1 and the transactivating domain of EWS but loses most of the regulatory domains of both proteins (6). Therefore, this protein is constitutively active and alters the expression of more than 500 genes (7). The resulting genetic program is believed to drive malignant transformation and clearly plays a central role in mediating the oncogenic phenotype (8-10). Most notably, EWS-FLI1 has been shown to directly or indirectly mediate the evasion of apoptosis and senescence, drive proliferation and even participate in the regulation of genes involved in metastasis (11-15). In addition, multiple groups have shown that knockdown of EWS-FLI1 with antisense DNA, siRNA or dominant negative methods is incompatible with ESFT cellular survival (16). Therefore, recent preclinical efforts have been focused on developing a small molecule therapy targeting this transcription factor (17, 18). Unfortunately, previously identified small molecule inhibitors have failed to demonstrate clinical activity against ESFT (19).

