2 ELIGIBILITY ASSESSMENT AND ENROLLMENT

2.1 ELIGIBILITY CRITERIA

2.1.1 Inclusion Criteria

2.1.1.1 Diagnosis

Patient's current disease state must be one for which there is no known curative therapy or therapy proven to prolong survival with an acceptable quality of life.

Phase I Portion: Measurable or evaluable refractory or recurrent extracranial solid tumors, excluding brain tumors and cerebral metastases.

Phase II Portion adults and children: Refractory or recurrent extracranial Ewing sarcoma with EWS-FLI1 fusion transcript. Patients enrolled to this cohort must have measurable disease. Presence of the transcript will be determined during histologic confirmation of disease with a CLIA approved EWS-FLI paraffin assay in the Laboratory of Pathology CCR, NCI, unless a pathology report documenting presence of the transcript using a CLIA approved assay is obtained from the referring institution.

2.1.1.2 Histologic confirmation of disease in the Laboratory of Pathology, CCR, NCI, NIH.

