2.2.3 Radiographic Evaluation

Assessment of disease sites by appropriate radiological evaluation. This could include a CT scan of chest, abdomen and pelvis and primary tumor, and bone scan, FDG-PET or MRI as indicated. A consistent method of disease evaluation for each patient will be used throughout the study.

Imaging of the head/brain to rule out intracranial disease including brain metastases is not required in all patients, but should be performed if there is clinical concern for intracranial disease/brain metastases

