6.2.3 Measurable Disease

Measurable lesions are defined as those that can be accurately measured in at least one dimension (longest diameter to be recorded) as ≥ 20 mm by chest x-ray, as ≥ 10 mm with CT scan, or ≥ 10 mm with calipers by clinical exam. All tumor measurements must be recorded in millimeters (or decimal fractions of centimeters).

Note: Tumor lesions that are situated in a previously irradiated area might or might not be considered measurable. *If the investigator thinks it appropriate to include them, the conditions under which such lesions should be considered must be defined in the protocol.*

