6.2.6 Target Lesions

All measurable lesions up to a maximum of 2 lesions per organ and 5 lesions in total, representative of all involved organs, should be identified as **target lesions** and recorded and measured at baseline. Target lesions should be selected on the basis of their size (lesions with the longest diameter), be representative of all involved organs, but in addition should be those that lend themselves to reproducible repeated measurements. It may be the case that, on occasion, the largest lesion does not lend itself to reproducible measurement in which circumstance the next largest lesion which can be measured reproducibly should be selected. A sum of the diameters (longest for non-nodal lesions, short axis for nodal lesions) for all target lesions will be calculated and reported as the baseline sum diameters. If lymph nodes are to be included in the sum, then only the short axis is added into the sum. The baseline sum diameters will be used as reference to further characterize any objective tumor regression in the measurable dimension of the disease.

Progressive disease by RECIST criteria [1] noted after the first re-staging scan may represent disease that was not detected on the pre-study scan, and a confirmatory scan will be required at the next scheduled re-staging evaluation unless clinically not indicated. If confirmed, progression should be dated by the initial time when the lesions are first detected. If progressive disease by RECIST criteria is seen after cycle 2, but not confirmed on subsequent restaging scan, the scans from after cycle 2 would serve as the baseline scan to evaluate for disease progression (49).

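### Sections 6.2.3 and 6.2.5 class a CT-measurable soft-tissue mass arising from bone in opposite ways, and phase II eligibility and partial response depend on the class.

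*Combined protocol and SAP*

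**What the plan says.** Section 6.2.3 sets the test: "Measurable lesions are defined as those that can be accurately measured in at least one dimension", with thresholds of 20 mm on chest x-ray, 10 mm on CT and 10 mm by calipers. It names no excluded site.

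Section 6.2.5 then lists disease that is not measurable. The list begins "Bone lesions, leptomeningeal disease, ascites, pleural/pericardial effusions" and ends "abdominal masses (not followed by CT or MRI), are considered as non-measurable". The words in brackets stand next to abdominal masses. Bone lesions carry no size, imaging or soft-tissue qualifier.

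The class decides three things in phase II:

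- **Eligibility.** Section 2.1.1.1: "Patients enrolled to this cohort must have measurable disease". Phase I is looser: "Measurable or evaluable refractory or recurrent extracranial solid tumors".
- **Target selection.** Section 6.2.6 draws target lesions from "All measurable lesions up to a maximum of 2 lesions per organ and 5 lesions in total". Under 6.2.7 everything else is non-target and need not be measured.
- **Partial response.** Section 6.2.1.1 defines PR as a fall of at least 30% in the summed diameters of target lesions.

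The only rule specific to bone, 6.2.8, covers progression on bone scan and does not mention measurability or response. Section 1.2.1 says of the disease that it "is the second most common malignant bone tumor of childhood", and 2.2.3 says of the imaging work-up: "This could include a CT scan of chest, abdomen and pelvis and primary tumor".

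**The concern.** The primary phase II endpoint is objective response in a tumour that the protocol itself describes as a bone tumour. If a measurable mass arising from bone is treated as non-measurable, two things can happen. A patient with no other measurable lesion fails phase II entry. A patient who does enter on other lesions has the mass followed only as non-target disease, so its shrinkage cannot produce a PR.

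The response counts that drive decisions are small. Stage 1 stops at 0 of 9 and continues at 1 of 9; the final analysis separates 2 from 3 responses in 24. One patient whose response turns on which section the assessor followed can change either decision.

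**Working it through.** **1. The plan's own design figure.** Section 8.2 gives p0 = 0.05, p1 = 0.25, stop at 0 of 9, success at 3 or more of 24, and 63% early termination under the null.

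- Early termination under p0: 0.95^9 = 0.630, as stated.
- Probability of success = sum over x from 1 to 9 of Bin(9, p)(x) × P(Bin(15, p) ≥ 3 − x). At p = 0.05 this is 0.093, within the planned 0.10. At p = 0.25 it is 0.903, which meets the planned 0.90.
- A grid search for the smallest expected sample size under p0 returns this same design.

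The sample-size section is correct. The issue lies in how a response is classified before it is counted.

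**2. The same lesion under each section.** Take a lesion arising from bone with a soft-tissue mass of 80 mm, accurately measurable on CT. The size is illustrative.

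| Question | Following 6.2.3 | Following 6.2.5 literally |
|---|---|---|
| Measurable? | Yes (80 mm ≥ 10 mm on CT) | No (bone lesion) |
| Phase II entry if it is the only disease | Meets the measurable-disease criterion | Fails it |
| May be a target lesion (6.2.6) | Yes | No |
| Must be measured at follow-up (6.2.7) | Yes, if chosen as a target | No |

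**3. Effect on scoring.** Add an 11 mm lung nodule, which is measurable, so the patient is eligible either way. Percent change = (follow-up sum − baseline sum) / baseline sum.

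*Mass shrinks from 80 to 40 mm, nodule unchanged:*
- Mass as target: (40 + 11 − 91) / 91 = −40/91 = −44%. This passes the 30% threshold: PR, if confirmed.
- Mass as non-target: (11 − 11) / 11 = 0%. Stable disease.

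*Nodule shrinks from 11 to 7 mm, mass unchanged:*
- Mass as target: (80 + 7 − 91) / 91 = −4/91 = −4%. Stable disease.
- Mass as non-target: (7 − 11) / 11 = −36%. With the non-target mass persisting but not progressing, the table in 6.2.1.1 gives PR, if confirmed.

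So the classification can remove a response or create one; the direction is not fixed.

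**4. What non-target status still does.** Under 6.2.1.1 a persisting non-target lesion prevents complete response, and its unequivocal progression is progressive disease. That standard asks for a change in overall disease status rather than growth of a single lesion. New bone-scan lesions count under 6.2.8. The mass is therefore left out of the target sum, but not out of response assessment.

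**5. What cannot be computed.** No section gives the share of patients with bone-only or bone-based measurable disease. Any figure for screen failures, accrual or power would only restate an assumed share, so none is given.

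**The case against.** The best reply is that the sections can be reconciled. Section 6.2.5 begins by describing itself as the residual class, so a mass that already passes 6.2.3 might never reach it. The measurement rules in 6.2.1.1 are headed as applying to soft tissue, while 6.2.8 treats bone lesions as bone-scan findings. On that view a soft-tissue mass is measured as soft tissue wherever it arises. This reading is sensible and may be what the authors meant, but no section states it, and the separate sentence that names bone lesions contradicts it on its face.

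A second reply is that RECIST 1.1 is the adopted standard and would settle the matter. The note at the start of 6.2, however, tells readers to class lesions by the criteria printed in that section, and the cited guideline is not among the documents.

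A third is that the CT/MRI words in 6.2.5 qualify the whole list. They fit ascites and leptomeningeal disease poorly, and that reading would itself need stating.

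A fourth has some force: the trial is single-institution and 6.2.2 has responses confirmed centrally, which limits disagreement between readers. But the studies sent for confirmation are those already scored as PR or complete response. That step does not address entry decisions or recover a response that was never scored.

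It also stands that no section describes Ewing bone lesions as carrying a measurable soft-tissue mass. The point is conditional on such a lesion presenting.

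**Conclusion.** The conflict is real and worth correcting. For a bone-based lesion with a soft-tissue mass accurately measurable at 10 mm or more on CT, 6.2.3 and 6.2.5 give opposite labels, and in phase II the label controls entry, target selection and PR. For a single patient the effect can be the whole outcome: -44% against 0% in the example, PR against stable disease.

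A reader might infer more than the documents support:

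- *That accrual is slowed or power is lost by a stated amount.* The affected share is not given. The 1-2 patients per month in section 8.6 is accrual for the whole study, not a phase II screening rate. If such patients are simply excluded at entry, the operating characteristics of the two-stage design do not change.
- *That bone disease is ignored.* It still bears on complete response and progression as non-target disease.
- *That patients with bone disease cannot enter.* Those with another measurable lesion meet the phase II criterion, and phase I accepts evaluable disease.
- *That the sample size is wrong.* It reproduces.

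The conclusion rests on the literal wording of 6.2.5. If the sponsor always meant 6.2.3 to govern, the remedy is the same: say so.

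**What to change.** 1. In 6.2.5, replace the entry for bone lesions with: *bone lesions without a soft-tissue component that meets 6.2.3*.
2. In 6.2.3, add that the soft-tissue component of a bone lesion is measurable when it meets the same size test as any other lesion, and may then be a target lesion subject to the reproducibility rule in 6.2.6.

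If MRI measurement is to be allowed, put one MRI threshold in 6.2.3 for all lesions. Section 6.2.10 names MRI alongside CT for measuring target lesions, but 6.2.3 gives no MRI threshold. Adding one for bone-based masses alone would create a new inconsistency with masses outside bone.

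The cost is two sentences in an amendment, with a third if MRI is included. Under the CT rule the same scans and readers are used. The downside is small: margins at bone can be harder to measure, and 6.2.6 already directs readers to lesions that can be measured reproducibly.

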6.2.6 Target Lesions

All measurable lesions up to a maximum of 2 lesions per organ and 5 lesions in total, representative of all involved organs, should be identified as **target lesions** and recorded and measured at baseline. Target lesions should be selected on the basis of their size (lesions with the longest diameter), be representative of all involved organs, but in addition should be those that lend themselves to reproducible repeated measurements. It may be the case that, on occasion, the largest lesion does not lend itself to reproducible measurement in which circumstance the next largest lesion which can be measured reproducibly should be selected. A sum of the diameters (longest for non-nodal lesions, short axis for nodal lesions) for all target lesions will be calculated and reported as the baseline sum diameters. If lymph nodes are to be included in the sum, then only the short axis is added into the sum. The baseline sum diameters will be used as reference to further characterize any objective tumor regression in the measurable dimension of the disease.

Progressive disease by RECIST criteria [1] noted after the first re-staging scan may represent disease that was not detected on the pre-study scan, and a confirmatory scan will be required at the next scheduled re-staging evaluation unless clinically not indicated. If confirmed, progression should be dated by the initial time when the lesions are first detected. If progressive disease by RECIST criteria is seen after cycle 2, but not confirmed on subsequent restaging scan, the scans from after cycle 2 would serve as the baseline scan to evaluate for disease progression (49).

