6.2.1 Response Criteria for Radiographic Studies

6.2.1.1 Measuring of Soft Tissue Disease

Response and progression will be evaluated in this study using the new international criteria proposed by the revised Response Evaluation Criteria in Solid Tumors (RECIST) guideline [version 1.1 (48)]. Changes in the largest diameter (unidimensional measurement) of the tumor lesions and the shortest diameter in the case of malignant lymph nodes are used in the RECIST criteria.

a. Evaluation of Target Lesions

Complete Response (CR)

Disappearance of all target lesions. Any pathological lymph nodes (whether target or non-target) must have reduction in short axis to <10 mm

Partial Response (PR)

At least a 30% decrease in the sum of the diameters of target lesions, taking as reference the baseline sum diameters

Progressive Disease (PD)

At least a 20% increase in the sum of the diameters of target lesions, taking as reference the smallest sum on study (this includes the baseline sum if that is the smallest on study). In addition to the relative increase of 20%, the sum must also demonstrate an absolute increase of at least 5 mm. (Note: the appearance of one or more new lesions is also considered progressions)

Stable Disease (SD)

Neither sufficient shrinkage to qualify for PR nor sufficient increase to qualify for PD, taking as reference the smallest sum diameters while on study

b. Evaluation of Non-Target Lesions

Complete Response (CR)

Disappearance of all non-target lesions and normalization of tumor marker level. All lymph nodes must be non-pathological in size (<10 mm short axis)

Note: If tumor markers are initially above the upper normal limit, they must normalize for a patient to be considered in complete clinical response.

Non-CR/Non-PD (Stable Disease, SD)

Persistence of one or more non-target lesion(s) and/or maintenance of tumor marker level above the normal limits.

Progressive Disease (PD)

Appearance of one or more new lesions and/or *unequivocal progression* of existing non-target lesions. *Unequivocal progression* should not normally trump target lesion status. It must be representative of overall disease status change, not a single lesion increase.

Although a clear progression of “non-target” lesions only is exceptional, the opinion of the treating physician should prevail in such circumstances, and the progression status should be confirmed at a later time by the review panel (or Principal Investigator).

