c. Evaluation of Best Overall Response

The best overall response is the best response recorded from the start of the treatment until disease progression/recurrence (taking as reference for progressive disease the smallest measurements recorded since the treatment started). The patient's best

response assignment will depend on the achievement of both measurement and confirmation criteria.

Target Lesions	Non-Target Lesions	New Lesions	Overall Response	Best Overall Response when Confirmation is Required*
CR	CR	No	CR	≥ 4 wks. Confirmation**
CR	Non-CR Non-PD	No	PR	≥ 4 wks. Confirmation**
CR	Not evaluated	No	PR	
PR	Non-CR Non-PD Not evaluated	No	PR	
SD	Non-CR Non-PD Not evaluated	No	SD	Documented at least once ≥ 4 wks. from baseline**
PD	Any	Yes or No	PD	No prior SD, PR or CR
Any	PD***	Yes or No	PD	
Any	Any	Yes	PD	

*See RECIST 1.1 manuscript for further details on what is evidence of a new lesion.
**Only for non-randomized trials with response as primary endpoint.
***In exceptional circumstances, unequivocal progression in non-target lesions may be accepted as disease progression

- d. Patients with a global deterioration of health status requiring discontinuation of treatment without objective evidence of disease progression at that time should be reported as “*symptomatic deterioration*.” Every effort should be made to document the objective progression even after discontinuation of treatment.
- e. In some circumstances, it may be difficult to distinguish residual disease from normal tissue. When the evaluation of complete response depends on this determination, it is recommended that the residual lesions be investigated (fine needle aspirate/biopsy) before confirming the complete response status.

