6.2.8 Metastatic Bone Lesions

Disease progression is considered if a minimum of two new lesions is observed on bone scan. New lesions seen by the end of cycle 2 or before cycle 3 (with the first re-staging bone scan) may represent disease that was not detected on the pre-study scan, and a confirmatory scan will be required at the next scheduled re-staging bone scan unless clinically not indicated. If confirmed, progression should be dated by the initial time when the lesions are first detected. If new lesions are seen after cycle 2, but no additional lesions are seen on confirmatory scans, the scans from post-cycle 2 would serve as the baseline scan to evaluate for disease progression (49).

Clinical Lesions

Clinical lesions will only be considered measurable when they are superficial (e.g., skin nodules and palpable lymph nodes) and ≥ 10 mm diameter as assessed using calipers (e.g., skin nodules). In the case of skin lesions, documentation by color photography, including a ruler to estimate the size of the lesion, is recommended.

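### Section 6.2.6 re-baselines any unconfirmed first-restaging progression, including growth of target lesions already measured, against the smallest-sum reference in 6.2.1 and 6.2.2

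*Combined protocol and SAP*

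**What the plan says.** **General rule.** Section 6.2.1.1(a) defines PD as a rise of at least 20% and 5 mm over the smallest on-study sum, and adds that "the appearance of one or more new lesions is also considered progressions". It asks for no confirmation of PD. Section 6.2.1.1(c) sets the response window: "The best overall response is the best response recorded from the start of the treatment until disease progression/recurrence". How PD is to be judged within that window is also laid down there, namely by "taking as reference for progressive disease the smallest measurements recorded since the treatment started". Section 6.2.2(b) ends duration of response by the same reference. None of these makes an exception for a reset baseline.

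**Special rule.** Section 6.2.6, headed Target Lesions, says: "Progressive disease by RECIST criteria [1] noted after the first re-staging scan may represent disease that was not detected on the pre-study scan". A confirmatory scan is then due at the next restaging, unless there is a clinical reason not to do it. For confirmed PD: "If confirmed, progression should be dated by the initial time when the lesions are first detected". For PD that is not confirmed: "the scans from after cycle 2 would serve as the baseline scan to evaluate for disease progression (49". Regression is still measured from the original baseline sum.

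**Bone scans.** Section 6.2.8 has a parallel rule: "Disease progression is considered if a minimum of two new lesions is observed on bone scan". On confirmation it adds a condition, "If new lesions are seen after cycle 2, but no additional lesions are seen on confirmatory scans"; in that case the post-cycle-2 scan again becomes the progression baseline.

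**Analysis and treatment.** Section 8.2.1 names disease progression as a TTP event, uses Kaplan-Meier and reports 6-month PFS. Section 8.3 sets a six-cycle window for best response. Neither cites 6.2.1 or 6.2.6. Scans follow every even cycle (3.5.1.5). Section 3.4 allows another cycle only if disease is stable or responding. Section 3.7.1(6) removes patients with PD as Section 6.2 defines it.

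**The concern.** Take a patient whose target lesions grow enough to meet PD after cycle 2 and fall just below the threshold after cycle 4. Under 6.2.1 the event is at the first restaging. Under 6.2.6 there is no event, and the enlarged post-cycle-2 scan becomes the yardstick for later progression. The stated justification does not reach this case, because a lesion measured at baseline was not missed at baseline.

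The stake is the meaning of TTP and 6-month PFS. Raising the reference after growth makes later progression harder to declare, and the shift goes one way for every affected patient. Sections 6.2.1.1(c) and 6.2.2(b) meanwhile keep the smallest measurements as reference, so the same scans can be classified differently depending on the section applied. It is also unclear whether such a patient is dosed while the confirmatory scan is awaited.

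**Working it through.** **1. The plan's own figures (8.2).** Stop if 0 of 9 respond; declare activity if 3 or more of 24 respond; p0 = 0.05, p1 = 0.25.
- Early termination under p0 = 0.95^9 = 0.630 (stated: 63%).
- P(declare activity) = sum over x = 1 to 9 of P(X = x) × P(Y ≥ max(0, 3 − x)), with X ~ Bin(9, p) and Y ~ Bin(15, p). This gives 0.093 at p = 0.05 (limit 0.10) and 0.903 at p = 0.25 (target 0.90).

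The design reproduces. The problem lies in the endpoint definition.

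**2. PD threshold after re-baselining.** Let B be the baseline sum, which is the smallest sum at the first restaging. PD after cycle 2 by target growth needs a sum of at least 1.2B. If that sum is the new reference, the next threshold is at least 1.2 × 1.2B = 1.44B, a minimum. With B = 100 mm and assumed post-cycle-2 sums:

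| Post-cycle-2 sum (mm) | Next threshold, 6.2.6 (mm) | Threshold, 6.2.1 (mm) |
|---|---|---|
| 120 | 144 | 120 |
| 125 | 150 | 120 |
| 130 | 156 | 120 |
| 150 | 180 | 120 |

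Example: 100 mm, then 125 mm (+25%), then 115 mm (+15%, so not confirmed). Under 6.2.1 the event is after cycle 2. Under 6.2.6 there is none, and the next threshold is 150 mm. If the later 115 mm were taken as a new smallest sum after the reset, it would be 1.2 × 115 = 138 mm, still above 120.

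**3. Timing.** With 28-day cycles, scans fall at about days 56, 112 and 168. An unconfirmed day-56 PD can become an event no earlier than the next scheduled scan: 112 − 56 = 56 days later. If day 112 shows no PD of any kind, the delay is at least 168 − 56 = 112 days. Confirmed PD is back-dated and does not move.

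**4. 6-month PFS (about day 183).** The estimate changes fully only if the patient also has no PD at days 112 and 168.
- Without censoring: 0 to 1/24 = 4.2 points per affected patient, or 0 to 1/9 = 11.1 points if the trial stops at 9.
- With 4 patients censored before day 56 (assumed): up to 1/20 = 5.0 points. With 8 (assumed): 1/16 = 6.25 points.
- Direction: each patient's own event time can only move later. If others are censored between the two dates and the delayed event still falls before 6 months, the Kaplan-Meier step is taken over fewer patients. For example, 23/24 = 0.958 becomes 19/20 = 0.950 with 4 censored in between. The one-way statement about 6-month PFS therefore assumes no censoring between scans.

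**5. Primary endpoint.** PR is judged from B, so moving from PD by target growth to PR means going from at least 1.2B to at most 0.7B. That is a fall of at least 1 − 0.7/1.2 = 41.7%. On scheduled scans it needs PD at day 56, PR at day 112 and confirmation at day 168, inside the six-cycle window. It matters to the decision only if this patient is the sole responder among the first 9 or the third among 24.

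**The case against.** **Specific over general.** Sections 6.2.6 and 6.2.8 belong to Section 6.2 and say how progression is dated, which serves a time-to-event endpoint. A reader might infer that the plan leaves it wholly open whether these rules feed TTP. The documents do not support that: the dating language indicates that they do. This part of the objection stands. It does not remove the conflict with the unqualified smallest-measurement wording in 6.2.1.1(c) and 6.2.2(b).

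**Target growth was not intended.** The rationale and the dating sentence both speak of detecting lesions, which does not describe growth of a known one. That is good evidence of intent and supports the narrow fix. The text, though, sits under Target Lesions and refers to PD by RECIST without limit, so as worded it applies.

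**Bone lesions.** A reader might infer that the two-lesion bone criterion contradicts the one-lesion rule. But the latter appears under a soft-tissue heading, and 6.2.5 treats bone lesions as non-measurable. A separate bone-scan rule is defensible. It also lets a target PR at day 56 stand beside new bone lesions that are set aside, with confirmation at day 112. That follows from a rule worth keeping.

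**A broader remedy.** One could confine 6.2.6 and 6.2.8 to treatment decisions and not count responses after unconfirmed PD. That would count disease present but undetected before the study as progression. If 10% of responders followed that path (assumed), 25% becomes 22.5% and power falls from 0.903 to 0.862. The documents give no reason to pay that price.

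**Conclusion.** Section 6.2.6 is wrong as written on one point: it raises the PD reference after unconfirmed growth of target lesions, against 6.2.1 and 6.2.2 and beyond its own rationale. The later threshold is at least 1.44 times the original reference, against 1.2, if the cycle-2 sum is used.

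The consequence is modest. TTP is a preliminary secondary objective (1.1.2.4) and no test is attached to it or to 6-month PFS. The documents give no rate of unconfirmed PD, and the effect is zero if every first PD is confirmed. The sizes above rest on nominal 28-day cycles, scans on schedule and the stated censoring assumptions.

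A reader might infer that the primary result is in danger. The documents do not support this: the path through target growth is narrow and should be rare, although cut-offs of 0/9 and 3/24 can in principle turn on one patient.

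**What to change.** - In 6.2.6, limit re-baselining to new lesions that may have been present but undetected before the study. Keep the smallest on-study sum as the PD reference for target lesions at all times.
- In 8.2.1 and 8.3, cross-refer to this rule for TTP, 6-month PFS and the best-response window.
- Leave the bone-scan rule in 6.2.8 as it is.
- Report TTP and 6-month PFS under the unmodified 6.2.1 definition, dated at first documentation, as a sensitivity analysis.
- Make 3.4 and 3.7.1(6) agree with 6.2.6 and 6.2.8 on whether dosing continues until the confirmatory scan.

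The cost is rewording and one extra analysis, with no added scans or patients. TTP and PFS may look slightly less favourable, and a patient whose target growth later reverses will count as progressed at the first restaging.
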